**Design**

Please provide a lay summary (written at 6th grade level) that includes a statement about the purpose and the general aims of the research.

Dysphagia (difficulty swallowing) is common following anterior cervical spine surgery. Studies have documented persistent swallowing difficulty up to two years postoperatively. The long term objective is to change the treatment paradigm for cervical spine surgery to minimize dysphagia and associated complications. The specific aims are to identify the effect of a single dose of perioperative steroid on dysphagia and to develop a treatment protocol for the frequency of perioperative steroids needed to reduce dysphagia. This is a prospective, randomized, placebo-controlled study. Patients will be given a single dose of dexamethasone or normal saline intratoperatively and then assessed at multiple time points up to one year. The research question is what is the effect of a single dose of perioperative steroid on dysphagia after anterior cervical spine surgery? The survey instruments used to determine difficulty swallowing include the Bazaz, Dysphagia Short Questionnaire, and EAT 10. To administer the Bazaz instrument, the study coordinator will ask the subject if he/she has difficulty swallowing liquid food and give the options 'none', 'rare', 'present all the time'. The options for solid food are 'none', 'rare', 'occasional only with specific foods', or 'frequent majority of solids'. The options on the left side of the questionnaire determine the level of difficulty. If a subject has no difficulty swallowing both liquid and solid food, 'none' will be chosen. The level of difficulty swallowing is determined by the highest difficulty, e.g. if a subject had no difficulty swallowing liquid food and has rare difficulty swallowing solid food, 'mild' will be chosen. If the subject has no difficulty swallowing liquid food but has frequent difficulty swallowing solid food, 'severe' will be chosen.

Fully describe all procedures to be performed, from start to finish, numbering your procedures 1,2,3 or A, B, C (e.g., 1. Recruiting, 2. Consent, 3. Collecting data, 4. How findings will be shared, etc.).

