Swallowing symptoms will be measured using the patient reported Bazaz Dysphagia Scale, EAT-10 survey, and the Dysphagia Short Questionnaire. Swallowing data will be obtained pre-operatively, one and two days post-operatively and then one week, two weeks, four weeks, three months, six months, and one year post-operatively. Scores from the Bazaz Dysphagia Scale and the Dysphagia Short Questionnaire from the two groups will be compared at the various time points using the Mann-Whitney U test. Power and sample size calculations are based on the presence or absence of dysphagia at two weeks. Based on a literature review, we postulated that 50% of the patients in the control group would experience mild, moderate, or severe dysphagia. If that figure can be improved to the point where just 20% of the patients are similarly affected then that, in our opinion, would represent clinical success. Under the above scenario, 32 patients in each group would give us 81% power to reject the null hypothesis. Assuming a dropout rate of 20% our total sample size for the study is 80. Statistical significance is set at  $p < 0.05$ . We plan to analyze the data in three ways. First, we will look at the time-to-event where the event is "no dysphagia" in a discrete time survival model. Second, we will use a repeated measures ordinal categorical model to assess the effect of steroid/control in a generalized linear model. Lastly, we will compare the data from this study with that of our previous three-dose model to assess any difference in the degree of impact of the two dosing regimens.

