### Subjects

Indicate the maximum number of subjects to be enrolled or medical records to be reviewed at all sites by the WVU or VAMC research team.

80

Provide a rationale for choosing your sample size.

Scores from the Bazaz scale, the EAT-10, and the Dysphagia Short Questionnaire from the two groups will be compared at the various time points using the Mann-Whitney U test. Statistical significance is set at  $p<0.05$ . With a power of 0.80 and a clinical meaningful difference of 30% in scores, an estimated 32 patients per group is needed. However, based on a recent unpublished study at our institution, we expect a dropout rate of approximately 20%, and therefore plan for a total sample size for this study of 80 patients.

State the requirement(s) to become a participant in the study (e.g., age range, sex, language spoken, class enrollment/ranking).

Ages 18-80; undergoing elective ACDF, hybrid constructs, corpectomies, disc arthroplasty surgery

Explain why selection of participants will be equitable addressing gender, ethnicity, and/or race of subjects.

No one will be excluded based on gender, ethnicity or race. Exclusion criteria include: < 18 years of age; major trauma or neoplastic or infectious conditions requiring surgery. Also excluded will be patients undergoing anterior-posterior operations, those with a history of previous anterior cervical spine surgery, any patient requiring a halo vest, patients on chronic steroids, and patients remaining intubated post-operatively, and women who are pregnant.

In outline format and chronological order, describe what will be done to identify and recruit participants (e.g., A, B, C or 1, 2, 3).

1. Potential subjects will see Drs. [name], [name], [name], [name] or [name] at their History and Physical visit prior to elective anterior cervical spine surgery at the Spine Center. 2. Subjects will be told about the study at this visit, all questions will be answered by the surgeons and the research coordinator, all surveys that need to be completed will be shown to the potential subjects and they will be given the opportunity to consent. 3. If consented, the subject will be asked to complete baseline surveys (Bazaz, EAT-10 and Dysphagia Short Questionnaire) at this visit. 4. The subject will be randomized to receive either single dose steroid (dexamethasone) or saline (placebo) prior to surgery.

Will any of the subjects be less than 18 years old?

No

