### **Potential Benefits**

Is there any known benefit to the individual subject as a result of participating in the research? Payments to subjects should not be included in this section, but addressed in the Payments/Reimbursements section.

Potential benefit is less difficulty swallowing if the subject is assigned to the steroid group.

Describe the potential benefit(s) to society and/or scientific / medical knowledge of the planned work.

The results of this study will provide evidence for the use of steroids as a treatment for reducing the incidence and severity of dysphagia among patients undergoing anterior cervical spine surgery. A recently performed study at our institution has promising results from a three-dose regimen of steroids.

Similarly, two recent clinical studies have also shown decreased dysphagia with a multi-dose steroid regimen. If the hypothesis of this proposal is supported, the use of a single dose of perioperative steroid specifically lends itself well to application in patients undergoing these procedures in outpatient surgery centers, improving the safety of such procedures.

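### The stated 81% power at 32 per group needs a one-sided 5% test that the plan does not declare; two-sided, power is about 71–76%, or 62–64% with continuity-corrected or Fisher tests

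*Combined protocol and SAP*

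**What the plan says.** The answer on analysis methods in the Design section gives the sizing calculation. The endpoint is binary: "Power and sample size calculations are based on the presence or absence of dysphagia at two weeks". For the control arm, "we postulated that 50% of the patients in the control group would experience mild, moderate, or severe dysphagia". The target for the steroid arm follows: "If that figure can be improved to the point where just 20% of the patients are similarly affected". The result is "Under the above scenario, 32 patients in each group would give us 81% power to reject the null hypothesis". The same paragraph sets the significance threshold at p < 0.05 and raises the total to 80 for 20% dropout. It names no test for the two-week comparison of proportions and does not say whether the threshold is one- or two-sided.

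The sample-size rationale in the Subjects section reaches the same 32 and 80 by another description: "With a power of 0.80 and a clinical meaningful difference of 30% in scores, an estimated 32 patients per group is needed". This stands beside the Mann-Whitney U test, again with no sidedness.

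The wording on direction is mixed. The lay summary puts the research question without direction: "The research question is what is the effect of a single dose of perioperative steroid on dysphagia after anterior cervical spine surgery". It also aims to "develop a treatment protocol for the frequency of perioperative steroids needed to reduce dysphagia", and the Potential Benefits section speaks of "reducing the incidence and severity of dysphagia among patients undergoing anterior cervical spine surgery".

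**The concern.** Every input needed to check the 81% is printed except the test and its sidedness, and the answer turns on sidedness. A bare p < 0.05 is normally read as two-sided, and on that reading 81% looks too high for 50% versus 20% with 32 per group. Wording that hopes for a reduction in dysphagia does not declare a one-sided test.

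Two things are at stake. First, the enrolment of 80 rests on this figure. If the test is two-sided, the chance of missing the effect that the plan calls clinical success is about 27% (exact chi-square) or 36% (Fisher), not the implied 19%. Secondly, a one-sided 5% test has the same threshold in the favourable direction as a two-sided 10% test. If sidedness stays open, the criterion for success could be settled after results are known.

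**Working it through.** **Inputs, all from the Design section:** control rate 0.50, steroid rate 0.20, difference 0.30, 32 per group, level 0.05, dropout 20%. The mean rate is 0.35. The critical value is 1.645 one-sided and 1.960 two-sided.

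**Standard errors**
- Pooled: √(2 × 0.35 × 0.65 / 32) = 0.1192
- Unpooled: √((0.25 + 0.16) / 32) = 0.1132

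**Reproducing 81% (one-sided 5%)**
- Fully pooled: 0.30/0.1192 − 1.645 = 2.516 − 1.645 = 0.871, power 80.8%.
- Pooled z (pooled SE under the null, unpooled under the alternative): (0.30 − 1.645 × 0.1192)/0.1132 = 0.918, power 82.1%.

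**The same formulas, two-sided 5%**
- Fully pooled: 2.516 − 1.960 = 0.556, power 71.1%.
- Pooled z: (0.30 − 1.960 × 0.1192)/0.1132 = 0.586, power 72.1%.
- Unpooled z: 0.30/0.1132 − 1.960 = 0.690, power 75.5%.
- Continuity-corrected: (0.30 − 1/32 − 1.960 × 0.1192)/0.1132 = 0.310, power 62.2%.

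The chi-square, Fisher and mid-p figures below come from exact enumeration over two Binomial(32) arms.

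| Method, 32 per group | One-sided 5% | Two-sided 5% |
|---|---|---|
| Fully pooled | 80.8% | 71.1% |
| Pooled z | 82.1% | 72.1% |
| Arcsine | 82.4% | 73.0% |
| Chi-square, exact enumeration | 82.1% | 73.4% |
| Unpooled z | 84.3% | 75.5% |
| Mid-p | 81.2% | 72.3% (doubled) or 66.4% (minimum likelihood) |
| Log odds ratio (Wald) | 79.0% | 68.8% |
| Fisher | 74.8% | 64.4% |
| Continuity-corrected | 73.9% | 62.2% (63.1% by exact enumeration) |

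No two-sided method tried comes within 5 points of 81%. The two-sided level that would give 81% at 32 per group is 0.101 (fully pooled), 0.092 (pooled z), 0.090 (arcsine) or 0.076 (unpooled).

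**Size needed for two-sided 80% power, evaluable per group:** unpooled 36, arcsine 38, pooled z 39 (80.5%), exact chi-square 39 (81.3%), fully pooled 40, Fisher 44, continuity-corrected 45.

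**Dropout step:** 64/0.8 = 80, which is correct. For 39 evaluable per group, 39/0.8 = 48.75, so 49 per group and 98 in total. With 45 per group the total would be 114.

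**If all 80 were evaluable (40 per group):** two-sided power is 81.6% (pooled z) or 81.7% (exact chi-square).

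**The Subjects statement:** a 30% difference in scores cannot be checked, because no score distribution is given. Applied to the binary outcome, the Mann-Whitney test gives 73.4% two-sided at 32 per group, so it does not recover 0.80 either.

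**The case against.** The strongest reply is that 81% has not been shown to be wrong. The plan says only p < 0.05, a one-sided reading reproduces the figure, and two-sided is a convention that the reviewer supplies. That is fair as far as it goes: the stated power is conditional on an undeclared choice. It does not remove the need to declare that choice.

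The one-sided origin is also an inference. Two-sided power at 40 per group is 81.6%, so the figure may belong to the enrolled number before dropout. That explanation is open, but it does not rescue the sentence, which ties 81% to 32 per group and only then adds dropout.

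The two-sided ranges in the heading do not cover every method. The minimum-likelihood mid-p (66.4%) and the log-odds-ratio approximation (68.8%) fall between them. This stands and changes nothing, since all are well below 81%.

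Finally, the plan's three listed analyses are a discrete-time survival model, a repeated-measures ordinal model and a comparison with the previous three-dose study, with Mann-Whitney tests on scores. None is a two-week test of proportions. It is true that the figures here are not the power of any of those analyses. They do concern the only checkable basis given for enrolling 80. The attachments that the form mentions were not available, so the statement that no one-sided test is declared covers the supplied text only.

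**Conclusion.** The concern holds. At 32 evaluable per group and 50% versus 20%, 81% power requires an uncorrected or mid-p one-sided 5% test, and the supplied text declares none. On the conventional two-sided reading, power is about 73% for a chi-square test (71.1% to 75.5% across the usual uncorrected methods) and 62% to 64% with a continuity correction or Fisher's test. Neither the 81% in the Design section nor the 0.80 in the Subjects section is then met; 80% needs about 39 evaluable per group. The arithmetic is firm because it uses only printed inputs. The one assumption is that p < 0.05 is two-sided. The result concerns the sizing calculation alone; the power of the survival, ordinal and Mann-Whitney analyses cannot be derived from the documents.

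**What to change.** **Design section, analysis methods.** Name the sizing test and its sidedness and give the power that matches. Chi-square is used here as an example, to be replaced by the test actually intended.
- If two-sided, replace the 81% with: about 73% power (two-sided 5% chi-square, 32 evaluable per group; 80% is reached at about 39 evaluable per group).
- If one-sided was intended, declare it, justify it before unblinding, and state about 81–82% power (one-sided 5%). Say also whether the other analyses under the same p < 0.05 sentence are one-sided.
- In either case add: this is the basis for sizing, not the power of the survival, ordinal or Mann-Whitney analyses.

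**Subjects section, sample-size rationale.** Keep the Mann-Whitney sentence and reconcile the power statement with the Design section. If it is the same calculation, which the shared 32 and 80 suggest but do not prove, write: a 30-percentage-point difference in the proportion with dysphagia at two weeks (50% versus 20%), with the matching power. If it is a separate calculation on scores, give its test and score distribution.

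**Cost.** Wording in two sections and one sponsor decision on sidedness. Enrolment and data collection need not change. The price of the two-sided option is a stated power of about 73% and an explicit statement that 0.80 is not met at 32 evaluable per group. Holding two-sided 80% at the planned dropout would instead need about 98 enrolled. The price of the one-sided option is having to defend it.

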1. Potential subjects will see Drs. [name], [name], [name], [name] or [name] at their visit prior to elective anterior cervical spine surgery at the Spine or Neurosurgery Clinic. 2. Subjects will be told about the study at this visit, all questions will be answered by the surgeons and the research coordinator, all surveys that need to be completed will be shown to the potential subjects and they will be given the opportunity to consent. 3. If consented, the subject will be asked to complete baseline surveys (Bazaz, EAT-10, and Dysphagia Short Questionnaire) at this visit. The subject will also complete Standard of Care Patient Reported Outcome Measures (PROMS) at this visit. 4. The subject will be randomized to receive either single dose steroid (dexamethasone) or saline (placebo) prior to surgery. The dose is calculated based on body weight group will receive 0.3 mg/kg of intravenous dexamethasone (experimental group) 0.3 mg/kg saline (control group). The subject will not be charged for dexamethasone or saline. 5. The subject will undergo anterior cervical spine surgery per standard of care. 6. After administration of the antibiotics in the operating room, the single dose of steroid or saline will be given by the anesthesia team, who are blinded to the group assignment, via an intravenous bag (study drug) prepared by the investigational pharmacist, the only person who knows the group assignment. 7. The surgeon, patient, and research team are blinded to the group assignment. 8. The subject will be administered the surveys by phone call or in the hospital by the research coordinator on Day 1. 9. On Day 2, if the subject is still hospitalized, surveys will be administered by the research coordinator in the hospital or via phone call. 10. Following Day one surveys, and if the subject has been discharged, the subject will be called to complete the answers to the surveys via phone call at Day 2, Week 1, Week 2, Month 1, Month 3, Month 6 and Month 12. At Month 12, the subject will be asked to also complete standard of care PROMS. If the subject is in the clinic for follow up at the designated time frame for survey administration, the surveys will be completed in the clinic. If the subject is not in clinic at Month 12, the PROMS will be completed via phone call. 10. At the end of the study, all subjects will be called or mailed a letter indicating the group assignment they had been in. 11. Study Results will not be shared with the subjects.

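### Does the time-to-'no dysphagia' analysis need a rule for dysphagia that returns after a first 'none'?

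*Combined protocol and SAP*

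**What the plan says.** The analysis paragraph of the Design section gives the survival model one sentence: "we will look at the time-to-event where the event is 'no dysphagia' in a discrete time survival model". Nothing there or elsewhere says whether the event is the first or a lasting absence of dysphagia, or what happens if it returns.

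The lay summary in the same section defines the lowest Bazaz grade by the patient's state at one administration: "If a subject has no difficulty swallowing both liquid and solid food, 'none' will be chosen". The scale is given at eight post-operative visits: "one and two days post-operatively and then one week, two weeks, four weeks, three months, six months, and one year post-operatively".

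Two other planned analyses use the same data. Questionnaire scores are to be "compared at the various time points using the Mann-Whitney U test", and a repeated-measures ordinal model is listed second, after the survival model. The sample size rests on a single visit: "Power and sample size calculations are based on the presence or absence of dysphagia at two weeks".

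**The concern.** A patient can leave the grade none and re-enter it. A standard single-event discrete-time model removes the patient from the risk set at the first none, so later dysphagia does not enter that analysis. Someone free of symptoms on Day 1 and affected at Week 2 would be resolved on Day 1 in the survival model and a failure on the endpoint that sized the trial.

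Time to first none and time to lasting resolution are different quantities and can give different answers from the same data. A benefit confined to Days 1 and 2 could be described as faster resolution although the arms do not differ from Week 1 on. A benefit that begins at Week 1 would be diluted, because many patients already hold an event. The background stresses persistence ("Studies have documented persistent swallowing difficulty up to two years postoperatively") and follow-up runs to a year, so the lasting version is arguably the one of clinical interest.

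**Working it through.** **1. The plan's own figure.** The survival analysis has no stated figure. The only one nearby is 81% power with 32 per group for 50% against 20% dysphagia at Week 2. With pooled variance, power = Φ[(0.30 − z·√(2·0.35·0.65/32)) / √((0.25 + 0.16)/32)] = Φ[(0.30 − z·0.1192)/0.1132]. This is 82.1% at z = 1.645 (one-sided 5%) and 72.1% at z = 1.960 (two-sided). The stated figure is therefore matched to within about a point only one-sided; the plan does not state sidedness. Dropout: 64/0.8 = 80, as stated. Nothing below depends on this figure.

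**2. The mechanism.** Take an illustrative two-state process over the eight visits (assumed: 70% dysphagic on Day 1, 30% chance of resolving per visit). The share with a first none by Month 12 is 1 − 0.7 × 0.7⁷ = 94%, whatever the chance of return. The share actually dysphagic at Month 12 depends on that chance:

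| Chance of return per visit | 0% | 5% | 10% | 20% | 30% |
|---|---|---|---|---|---|
| Dysphagic at Month 12 | 6% | 17% | 26% | 40% | 50% |

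So the first-none event does not respond to relapse.

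**3. How many patients this touches.** The documents give no rate of return or late onset. Assume a latent normal process with correlation 0.6, 0.8, 0.9 or 0.95 between adjacent visits. The share of Week 2 cases who already hold an event is then:

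| Assumed control prevalence at Day 1, Day 2, Week 1, Week 2 | 0.6 | 0.8 | 0.9 | 0.95 |
|---|---|---|---|---|
| 70/70/60/50% | 41% | 25% | 13% | 6% |
| 50% throughout | 62% | 45% | 32% | 23% |

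With Week 2 prevalence at 50%, the shares of all patients are half of these: 21% to 3%, and 31% to 11.5%.

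**4. Would a lasting none be better?** Here lasting means none at every later completed visit, with at least one later visit to confirm it unless it occurs at Month 12. From the documents: 40 per arm, 20% dropout, and 50% against 20% at Week 2. Assumed: control prevalence 70/70/60/50/40/30/20/15% over the eight visits, and dropout uniform over the first seven. The model is a discrete-time logit with visit intercepts and arm, 1,000 trials per cell. Rejection rates at p < 0.05, for correlation 0.6/0.8/0.9/0.95:

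| True effect | First none | Lasting none |
|---|---|---|
| None | 4.8–6.3% | 5.4–5.8% |
| Days 1–2 only (70% to 40%) | 55/40/31/22% | 5/5/5/5% |
| Week 1 onward (steroid 30/20/15/12/8/6%) | 39/47/52/56% | 73/64/57/55% |
| Weeks 1–2 only | 26–27% | 5–7% |
| Day 1 to Week 2 (steroid 40/40/30/20%), then equal | 87/74/62/54% | 9/10/8/11% |
| Day 1 to Month 1, then equal | 88/82/67/58% | 14/16/16/16% |
| All visits (steroid 40/40/30/20/15/12/8/6%) | 93/88/82/81% | 81/76/74/74% |

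Repeat runs of several cells moved them by at most about 5 points and altered no conclusion.

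**5. Where later dysphagia is counted.** For a patient with none on Day 1 and dysphagia at Week 2:

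- Survival model, first none: event on Day 1; Week 2 not used.
- Mann-Whitney test at Week 2: counted at the observed grade.
- Repeated-measures ordinal model: both visits used.

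**The case for a change.** The strongest case for a change is that the event is undefined, that no analysis is named primary, and that this one is listed first. An analyst could choose between first and lasting none after seeing the data. The other analyses keep the later dysphagia but do not tell a reader what time to no dysphagia means. For an effect that starts at Week 1 and persists, the choice moves power from 39% to 73% at correlation 0.6. A definition would cost one sentence and one derived variable.

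The silence stands, and so does the divergence between definitions. The rest carries less weight. The missing primary analysis is a separate question that defining this event would not settle. An effect confined to Days 1 and 2 would show as such in the planned visit-by-visit comparisons, so reading it as durable resolution would mean ignoring results the plan already calls for. First none would also report correctly that patients were symptom-free sooner.

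A lasting none has difficulties of its own. It depends on later visits, and one late mild report delays the event. A patient who drops out straight after a single none must be either censored while symptom-free or counted on one visit (about 2.1 to 3.5 of 80 patients in the simulation). Patients who never had dysphagia still resolve on Day 1 under either definition.

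**Conclusion.** No change to the plan follows. The plan leaves a term undefined; it does not state a rule that gives a wrong result. The ordinary reading, first visit with none, is what most analysts would code. It holds its type I error near 5%, and the dysphagia it leaves out is counted in two other planned analyses.

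Making lasting none the main event is a choice on which reasonable statisticians would differ. It gains clearly in one of the scenarios tried, an effect from Week 1 that persists, and that gain is gone at correlation 0.95. It loses 7 to 12 points when the effect is present at every visit. It nearly misses an effect that runs from Day 1 to Week 2 and then fades (8–11% against 54–87%), although Week 2 is where the sponsor placed its definition of success. Reporting dysphagia by arm and visit would largely repeat comparisons already planned.

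Apart from the 50% and 20% at Week 2, the 80 patients and the 20% dropout, every simulation input is an assumption. Equal correlation between adjacent visits also ignores their very unequal spacing. The true rate of return is unknown, so the range of 6% to 62% shows only that the effect could be small or large. What remains is a detail that the analyst fixes when coding the event and that the trial report should state.

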Please describe the investigational procedures that will be performed throughout the duration of the study.

Randomization to steroids or no steroids for anterior spinal fusion subjects and completion of the Bazaz, Short Dysphagia Questionnaire and EAT-10 survey.

Please describe the standard of care procedures that will be performed throughout the duration of the study.

Everything outside of the randomization.

Will you be assigning or randomizing participants to groups or conditions (e.g., control, placebo)?

Yes

Describe the group assignment.

Random assignment to receive either one dose of steroid or one dose of saline (Placebo) during the first hour of surgery.

Does the research involve surveys/interviews/questionnaires? If so, attach a copy of the interview/survey questions on the Notes & Attachments page.

Yes

Will you be asking any questions that are likely to distress your subjects (e.g., questions about abuse, trauma, or suicide ideation)? If so, attach counseling services referral list on the Notes & Attachments page.

No

Describe what is known about this topic and why this study is needed. Please include at least two reference citations to support your rationale.  
See lit review and scientific rationale under Notes and Attachments.

What method are you going to use to analyze the data?

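### The single-dose versus three-dose comparison confounds regimen with study and does not require concurrent-control anchoring, so the trial cannot by itself deliver its dosing-frequency aim

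*Combined protocol and SAP*

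**What the plan says.** The lay summary in the Design section sets two specific aims. One is the effect of a single perioperative dose. The other is "to develop a treatment protocol for the frequency of perioperative steroids needed to reduce dysphagia". The design is described thus: "This is a prospective, randomized, placebo-controlled study". The group-assignment item gives the arms: "Random assignment to receive either one dose of steroid or one dose of saline (Placebo) during the first hour of surgery". There is no three-dose arm.

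The data-analysis item of the same section lists three analyses: a discrete-time survival model, a repeated-measures ordinal model for steroid versus control, and finally the cross-study comparison: "we will compare the data from this study with that of our previous three-dose model to assess any difference in the degree of impact". For this last analysis the plan states no endpoint, time point, model, covariates, role for the control arms, or expected precision.

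Of the three-dose study, the Potential Benefits section says only this: "A recently performed study at our institution has promising results from a three-dose regimen of steroids". Whether it was randomised, whether it had a control arm, its size and its event rates are not stated. The literature review and rationale are referred to attachments that are not part of the available documents.

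The sample size concerns a different comparison, single dose against placebo: "Power and sample size calculations are based on the presence or absence of dysphagia at two weeks".

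**The concern.** Every single-dose patient is in this trial and every three-dose patient is in the earlier one. Any difference between the studies in case mix, procedures, surgeons, period or survey practice therefore moves with regimen. If each regimen is first contrasted with its own concurrent control, a difference in background dysphagia risk largely cancels, at least on the scale on which the contrast is made. If the two steroid arms are compared directly, nothing cancels. The wording fits either analysis, so the choice could be made after the results are seen.

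No other planned analysis says anything about how often steroids should be given. Two unsupported conclusions are therefore possible: a cohort difference reported as a dosing effect, or an imprecise null reported as evidence that one dose does as well as three.

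**Working it through.** **1. The plan's own figure, and what it covers.** Inputs from the Design section: 50% dysphagia in controls ("50% of the patients in the control group would experience mild, moderate, or severe dysphagia"), the target that "just 20% of the patients are similarly affected", 32 per group, significance at 0.05 and 20% dropout.

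- SE under the null: √(2 × 0.35 × 0.65/32) = 0.1192.
- SE under the alternative: √((0.25 + 0.16)/32) = 0.1132.
- Two-sided power: Φ((0.30 − 1.96 × 0.1192)/0.1132) = 72.1%.
- One-sided power: Φ((0.30 − 1.645 × 0.1192)/0.1132) = 82.1%.
- Dropout: 64/0.8 = 80.

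The stated 81% is approached only with a one-sided 0.05 test. Sidedness is a separate matter and does not affect this point. What matters here is that the calculation covers single dose versus placebo and no figure covers the cross-study comparison.

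**2. Assumptions for the illustration.** The earlier study had a concurrent control, with 20, 32 or 50 evaluable patients per arm. Both studies have a 50% control rate and a 20% steroid rate. The outcome is dysphagia present or absent at two weeks. Only the rates and the 32 per arm in this trial come from the plan.

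**3. Anchored contrast (difference between the two steroid-minus-control risk differences).** SE = √(0.41/32 + 0.41/n), where 0.41 = 0.25 + 0.16 and n is the earlier study's size per arm.

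- n = 20: SE 0.183, 95% half-width 35.8 points.
- n = 32: SE 0.160, half-width 31.4 points.
- n = 50: SE 0.145, half-width 28.4 points.

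At n = 32, power to detect a 15-point difference between the regimens' effects is Φ(0.15/0.160 − 1.96) + Φ(−0.15/0.160 − 1.96), about 15%.

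**4. Direct contrast of the steroid arms.** SE = √(0.16/32 + 0.16/n). At n = 32 this is 0.100, half-width 19.6 points (22.3 at n = 20, 17.7 at n = 50). It looks tighter because the control arms are left out, and with them the protection against a background shift.

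**5. Effect of a background shift on the direct contrast.** Suppose the regimens are equally effective, but the control rate is 60% in one study and 50% in the other, with 32 per arm. The steroid rate in the 60% study depends on the scale on which the effect is constant:

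- Risk ratio 0.4: 0.4 × 60% = 24%.
- Odds ratio 0.25: odds 1.5 × 0.25 = 0.375, so 27.3%.
- Risk difference 30 points: 30%.

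Each is tested against 20% with SE = √(0.16/32 + p(1 − p)/32). The chance of a significant result is Φ(d/SE − 1.96) + Φ(−d/SE − 1.96), where d = p − 0.20:

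- 24%: SE 0.1034, false-positive rate 6.7%.
- 27.3%: SE 0.1058, rate 10.6%.
- 30%: SE 0.1075, rate 15.3%.

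The nominal rate is 5%.

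**The case against.** The strongest reply is that the plan is silent on anchoring and does not exclude it. This trial has a placebo arm, its data include that arm, and the degree of impact of a regimen reads naturally as its effect against control. The sentence just before also speaks of steroid against control. That stands: a reader might infer that the plan drops the placebo arms, but the documents show only that it does not require their use.

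A reader might also infer that the comparison can contribute nothing to the frequency aim. That goes too far. The stated research question is the single-dose effect, and nothing says this trial alone must settle frequency. An anchored comparison can give exploratory support.

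A third tempting inference is that the outpatient use mentioned under Potential Benefits would rest on a non-significant cross-study test. The text makes it conditional on the study's hypothesis being supported, which the randomised comparison addresses. No section says that non-significance will be read as equivalence. That is a risk to guard against, not a stated intention.

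The figures also have limits. The earlier study's design is unknown, a shared institution may keep differences small, and the 10-point shift has no source in the documents. The half-widths are for one binary time point and are not the precision of the planned repeated-measures ordinal model. Finally, the analysis is listed last and lies outside the power calculation. But it is not labelled exploratory, and the 0.05 threshold is stated without exempting it.

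None of this removes the confounding of regimen with study, which follows from the randomised arms alone.

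**Conclusion.** The point holds in this form: the cross-study comparison confounds regimen with study, the plan does not require anchoring to concurrent controls, and this is the only analysis bearing on frequency. The trial therefore cannot by itself deliver the frequency aim. The randomised comparison of single dose with placebo is unaffected.

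Under the stated assumptions, even the better, anchored version has a 95% half-width about equal to the whole effect the trial is designed to find. It could neither establish that one dose matches three nor reliably detect a moderate difference. The unanchored version is exposed to modest inflation of false positives if a 10-point shift acts on the risk-ratio scale, and to a threefold inflation if it passes one-for-one into the steroid arm.

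The confounding and the missing anchoring requirement rest on the text. The sizes rest on an assumed earlier study and would change with its true design. Anchoring is also not a full cure: the anchored contrast still mixes regimen with any difference between the studies in how well steroids work.

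**What to change.** Replace the last sentence of the data-analysis item in the Design section, before unblinding, with text to this effect:

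- The comparison with the three-dose study is exploratory.
- The outcome is dysphagia at two weeks, already the basis of the power calculation, analysed with the planned ordinal model.
- If the earlier study had a concurrent control and patient-level data are available, the model has study, treatment and study-by-treatment terms, adjusted for baseline score. The result reported is the difference between the within-study steroid-versus-control effects, with its 95% interval.
- If it had a concurrent control but patient-level data are unavailable, the reported within-study effects are compared.
- If it had no concurrent control, the comparison is descriptive only.
- The steroid arms are not tested directly against each other, and non-significance is not read as equivalence.
- The report states that the contrast still mixes regimen with between-study differences in effect. It also sets out how eligibility, procedures, instruments and assessment times compare across the two studies.

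In the lay summary, reword the second aim so that this trial estimates the single-dose effect against placebo and only informs later work on frequency.

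The cost is a few sentences and one additional model, with no extra patients or assessments. The downside is a weaker claim about dosing frequency.
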